Protocol Version 4.0
11May2017

Title:

Once-daily regimen with Envarsus® to optimize immunosuppression management and adherence in kidney transplant recipients

Institution:

Medical University of South Carolina

Principal Investigator:

[name]
Office: [contact]
[contact]
Email: [contact]

Sub-Investigators:

[name]
Office: [contact]
[contact]
Email: [contact]

[name]
Office: [contact]
[contact]

[name] [name]
Office: [contact]
Email: [contact]

1. Study Objectives

1. Primary objective

1. Estimate change from baseline to six months in adherence superiority measure by MMAS-8 in patients converted to a once-daily immunosuppressant regimen of Envarsus[®], everolimus, and prednisone versus patients converted to a twice-daily regimen of Envarsus[®] (once daily), MMF (twice daily), and prednisone (once daily).

2. Secondary objectives

1. Estimate the composite of treatment failure rate, defined as acute allograft rejection with a Banff grade 1A or higher, graft loss, or death at six months post-conversion, in patients converted to a once-daily immunosuppressant regimen of Envarsus[®], everolimus, and prednisone versus patients converted to a twice-daily regimen of Envarsus[®], MMF, and prednisone.

3. Outcomes 3.3.2 through 3.3.11 are considered exploratory

1. Examine subject specific change of the Memphis Medication Side Effect Scale (Appendix B2, 12) at the time of the conversion versus six months post-conversion, compared between the two arms (Appendix B2).
2. Examine subject specific change in quality of life, using the SF-36 (Appendix B3) at the time of conversion versus six months post-conversion, compared between the two arms.
3. Measure and compare time-to-event analysis of secondary objective between the two arms
 1. Patient death (time to event analysis)
 2. Biopsy proven acute rejection (Banff 1a or higher, time to event analysis)
 3. Graft loss (time to event analysis)
4. Examine the medication possession ratio (MPR) of adjunctive immunosuppressants (Everolimus or mycophenolate) during follow up between the two arms
 1. Compare the prevalence of patients with MPR >80%
5. Compare rates of adverse events and severe adverse events between the two arms
6. Perform exploratory analysis of subclinical rejection and IF/TA in patients with one year protocol biopsies as compared to three month protocol biopsies between the two arms

2. Background

1. Rationale

Non-adherence in renal transplant recipients has been widely reported, with conservative estimates reporting a prevalence between 20 and 67% (1,2). While it is difficult to determine the degree of nonadherence necessary to affect graft outcomes, there are several studies demonstrating the costs, with a graft loss rate 7 times greater than in adherent patients and an associated \$15-100 million annual costs. Due to the complex causes of nonadherence, no singular approach is likely to be effective (3). However, one of the most commonly cited reasons for nonadherence by patients is forgetfulness and disruptions in routine, with the evening dose of twice daily regimens the most likely to be affected (4). Tacrolimus LCP (Envarsus[®]) is a once-daily tacrolimus product that has demonstrated similar outcomes compared to twice-daily tacrolimus (tacrolimus IR) along with IL-2 receptor induction and mycophenolate mofetil adjunctive therapy with target concentrations of 4-11 ng/mL(5). In clinical trials that have studied the combination of tacrolimus and everolimus, such as the CRADO1AUS09 and ASSET studies, lower exposure to tacrolimus has demonstrated equivalent efficacy compared to standard

exposure tacrolimus, with a lower incidence of adverse effects. In these two studies, tacrolimus exposure after 3 months (the time of conversion for our study) was 4-6 ng/mL (US09) and 1.5-3 ng/mL (ASSET), both of which show adequate efficacy and safety in regards to biopsy-proven acute rejection (BPAR) and adverse events (6,7). Additionally, the currently enrolling TRANSFORM study (CRAD001A2433) utilizes a tacrolimus exposure of 2-5 ng/mL from month 2 to month 24 post-transplant. Envarsus, while demonstrating a unique drug-delivery profile, still maintains an equivalent correlation between exposure (AUC) and C0 values to tacrolimus IR, validating a low-exposure goal for Envarsus in combination with everolimus (8).

However, the combination of a once-daily product along with twice-daily products such as mycophenolate mofetil does not reduce the number of times per day immunosuppressive therapy is necessary. It has the potential, alternatively, to reduce adherence to the twice-daily product. Everolimus (Zortress®) is an mTOR inhibitor that has been studied and approved as an adjunctive immunosuppressant in kidney transplant recipients in a twice-daily regimen (6). However, due to the prolonged elimination half-life of everolimus (28±7 hours), a number of researchers have evaluated its ability to be used as a once-daily medication from a pharmacokinetic point of view. Kahan et al. demonstrated that, at steady state, the 24-hour AUC, Cmin, and Cmax increased proportionately to the administered dose. In addition, the relationship between the Cmin and the AUC after once-daily administration was excellent; confirming the ability to use Cmin levels to as an accurate predictor of drug exposure in once-daily everolimus regimens (9). Given this information, there have been subsequent clinical studies investigating a once-daily dosing interval with everolimus therapy. Carmellini et al. converted 12 patients to a once-daily regimen of everolimus and compared these patients to 12 subjects who maintained a twice-daily dosing regimen. The investigators demonstrated that conversion to once-daily everolimus in kidney transplant recipients did not significantly change their Cmin concentration. Further, there were no adverse events or acute rejection episodes 6 months after the conversion (12). In a larger study, Favi et al. compared 40 kidney transplant recipients randomized to once-daily everolimus with a target concentration of 2-6 ng/mL or twice-daily everolimus with a target concentration of 3-12 ng/mL. The investigators demonstrated equivalent renal function and acute rejection rates between the two groups, while the once-daily everolimus regimen demonstrated significantly improved cholesterol indices (13,14). In combination with tacrolimus-based regimens, it has also demonstrated excellent efficacy in preventing acute rejection, with significantly reduced tacrolimus exposure (goal trough concentrations: Everolimus 3-8 ng/mL) (6,7).

With the availability of well-studied once-daily formulations of tacrolimus, the ability to achieve a true once-daily immunosuppressant regimen along with Everolimus and steroids may finally be achievable and have the potential to optimize immunosuppression safety and efficacy in kidney transplantation.

2. Supporting data

1. 24-month, multinational open-label, randomized trial

	Everolimus 1.5mg per day with reduced exposure CsA N=277	Mycophenolic Acid 1.44 g per day with standard exposure CsA N=277
Efficacy Failure	70 (25.3)	67 (24.2)
Treated Acute Rejection	45 (16.2)	47 (17)
Death	7 (2.5)	6 (2.2)
Graft loss	12 (4.3)	9 (3.2)

	Everolimus 1.5mg per day with reduced exposure CsA N=277	Mycophenolic Acid 1.44 g per day with standard exposure CsA N=277
Any adverse reaction	271 (99)	270 (99)
Anemia	70 (26)	68 (25)
Leukopenia	8 (3)	33 (12)
Diarrhea	51 (19)	54 (20)
Nausea	79 (29)	85 (31)
Infections and infestations	169 (62)	185 (68)
UTI	60 (22)	63 (23)
URI	44 (16)	49 (18)
Blood creatinine increased	48 (18)	59 (22)
Hyperkalemia	49 (18)	48 (18)
Headache	49 (18)	40 (15)
Hypertension	81 (30)	82 (30)

2. Envarsus

	Envarsus XR +/- steroids, MMF/MPS or AZA N=162	Tacrolimus IR +/- steroids, MMF/MPS or AZA N=162
All infections	46%	48%
UTI	10%	14%
URI	26%	28%
BK virus	2%	2%
CMV	2%	1%
Serious Infections	8%	9%
NODAT	10%	11%
Diarrhea	14%	9%
Blood creatinine increased	12%	9%
Headache	9%	7%
Hypertension	4%	6%

	Envarsus XR +/- steroids, MMF/MPS or AZA N=162	Tacrolimus IR +/- steroids, MMF/MPS or AZA N=162
Treatment failure	4 (2.5%)	4 (2.5%)
BPACR	2 (1.2)	2 (1.2)
Graft failure	0	0
Death	2 (1.2)	1 (0.6)
eGFR at 12 months (ml/min)	62	61.4

3. In multiple chronic conditions it has been shown that once-daily regimens or dose reduction frequency through the selection of once-daily medications has improved adherence. Meta-analysis of medication adherence studies demonstrated that dose taking compliance decreases as medication regimens increase from QD, measured by MEMS (DOI: 10.1097/CRD.0b013e3180cabbe7).

TABLE 1. Rate of Adherence by Frequency of Regimen in Long-Term Clinical Treatment Studies

Frequency of Regimen	Mean Dose-Taking Compliance (%)	Standard Deviation (%)	Range (%)
QD (1 dose/d)	79	14	35-97
BID (2 doses/d)	69	15	38-90
TID (3 doses/d)	65	16	40-91
QID (4 doses/d)	51	20	33-81

This meta-analysis of 76 studies covered a range of therapeutic areas and included 26 cardiovascular studies (17 in patients with hypertension).

Adapted from Clinical Therapeutics, Vol. 23, Claxton AJ, Cramer J, Pierce C. A systematic review of the associations between dose regimens and medication compliance, pgs. 1296-1310, Copyright 2001, with permission from Excerpta Medica, Inc.⁴⁴

3. Study design
 1. Single-center, open-label, randomized comparative pilot trial.
 2. There will be 20 subjects in each arm, with a total study size of 40 subjects.
2. Allocation: Four random permuted-blocks of ten with equal arm allocation ratio will be used. Since no other stratification criteria are considered, larger block sizes will be appropriate. In each block, ten random numbers will be generated using SAS 9.4 with a range from zero to ninety nine. Even numbers will be assigned the intervention arm and odd numbers will be assigned the standard of care with resulting 1:1 allocation.
3. Intervention Model: Parallel assignment
4. Masking: This will be an open-label study as masking is not feasible given we are comparing twice-a-day to once-a-day regimen and its effect on adherence.
5. Selection and enrollment of subjects
 1. Inclusion criteria
 1. Male or female adult (≥ 18 years old) with a history of solitary kidney transplant within 3 months (± 2 months) of transplant.
 2. Patients must be capable of understanding the purposes and risks of the study and have the ability to give written informed consent and be willing to participate and comply with the study.
 3. Women of childbearing potential and sexually active males must be willing to use contraception, as indicated in Section 6 of the protocol. Subjects who are not of reproductive potential (status post bilateral tubal ligation, bilateral oophorectomy, hysterectomy, or vasectomy), not sexually active, whose current partner(s) is not of reproductive potential, or whose sexual activity is exclusively homosexual are eligible without requiring the use of contraception.
 2. Exclusion criteria
 1. Patients will be excluded if they are pregnant or nursing females or males with a pregnant female partner
 2. Recipient of multiple organ transplant
 3. Recipient of a non-renal organ
 4. Proteinuria > 800 mg/24 hour
 5. eGFR < 30 ml/min
 6. WBC $\leq 2k/mm^3$

7. $\text{Plt} \leq 50\text{k}/\text{mm}^3$
 8. Triglycerides $> 500 \text{ mg/dL}$
 9. HIV positive (HIV ab +)
 10. Unable to tolerate oral medications
 11. Use of another investigational product within thirty days prior to receiving study medication
 12. Acute graft rejection within the past month (Banff 1A or higher) or received an ABO incompatible donor organ.
 13. A condition or disorder that, in the opinion of the investigator, may adversely affect the outcome of the study or the safety of the subject
2. Study enrollment procedures
 1. Subject Identification/Recruitment: Members of the research team will identify potentially eligible patients who have undergone solitary kidney transplantation in the past three months (± 2 months). An initial evaluation of existing patient information may be performed to determine potential eligibility. This initial review may be performed prior to consent; however no protocol driven tests or procedures may be performed until signed informed consent has been obtained.
 2. Informed Consent: A qualified member of the research team, Human Subjects Protection Trained, will approach and explain the study and offer participation. The study will be explained in a manner consistent with the level of education pertaining to the patient. Enrollment procedure will involve face-to-face meetings of the patients to inform and review informed consent documentation. The participant will sign the consent form prior to evaluation of adherence measures. Copies of the informed consent will be appropriately placed in the corresponding chart and the patient will be provided with a copy of the signed consent form. Non-consenting individuals will also be ensured that no penalty will arise due to denying participation. Those who choose to participate in the trial will be informed that at any point they reserve the right to leave the study.
 3. Enrollment: Patients who give informed consent to study participation will go on to complete baseline procedures necessary to determine eligibility for randomization. Once deemed eligible for the study according to the inclusion/exclusion criteria, the patient will be enrolled as study participant. Information to be entered upon enrollment includes demographic information and date of transplant surgery. Enrolled subjects will be randomized to one of the treatment arms in the applicable cohort.
 4. Study interventions
 1. Interventions, administration, and duration
 1. For the first three months (± 2 months) post-transplant, the pool of patients from which subject of this study will be recruited will receive the current standard of care. Standard of care is described as a regimen of tacrolimus IR BID (5-12ng/mL) + MMF 1g BID + prednisone QD Three months (± 2 months) post-transplant and at the time of recruitment, they are randomized to one of the two arms to either receive a complete once-a-day regimen or to receive twice-daily regimen.
 2. Post-randomization, subjects will be converted to one of the two arms, as shown below, and followed for a total period of six months (primary endpoint), or until a terminal end point is reached.
 1. Arm 1: Control-- twice-daily regimen of Envarsus QD (5 - 12ng/mL) + MMF (goal dose 1g BID) + prednisone QD for 6 months

2. Arm 2: Intervention-- once-a-day regimen of Envarsus QD (2- 5ng/mL) + everolimus QD (3-8ng/mL) + prednisone QD for 6 months
 1. Envarsus will be supplied for both Arms from Veloxis Pharmaceuticals
2. Adherence assessment
 1. Adherence to the study intervention will be assessed at all study visits noted on the Schedule of Evaluations (Section 5.1), using the eight point Morisky Medication Adherence Scale (MMAS-8) (17).
5. Clinical and laboratory evaluations
 1. Schedule of evaluations

Data Collection Schedule

Report Form		Baseline	Days Post-Conversion							
			7±2	14±3	30±5	60±7	90±7	120±7	150±7	180±7
Informed Consent Obtained		X								
Randomization		X								
Review of Inclusion and Exclusion Criteria		X								
Medical History		X								
Kidney Transplant Recipient		X								
Vital Signs		X					X			X
Review of Medications and Dosing		X								
Clinical assessment*	Adverse events, dosage and adherence, rejection, infection, hospitalization				X	X	X	X	X	X
	MMAS-8, MMSE Scale, and SF36 (15,16,20)	X								X
Laboratory Assessments	CBC and Chem-7 ¹	X*	O	O	O	O	O	O	O	X*
	Everolimus CO ₂		X*	X*	X*	X*	X	X*	X*	X*
	Tacrolimus CO ₂	X*	X*	X*	X*	X*	X	X*	X*	X*
End of Study										X

X=required; O=optional: data will be collected if performed as standard of care; *=not current standard of care

Footnotes:

1. Includes sodium, potassium, chloride, CO₂, BUN, SrCr, glucose, calcium, WBC, HgB, Hct, platelets
2. Tacrolimus and Everolimus concentrations will be 12- or 24-hour levels , drawn in the morning of each assessment

2. Timing of evaluation
 1. Pre-Randomization Evaluations
Baseline

Evaluations listed under the baseline visit may be performed up to 14 days prior to randomization. Once the subject has been successfully screened and accepted for randomization, randomization must be completed within 48 hours.

2. Intervention and Evaluations

Once the subject has been successfully randomized, the patients will be directed to the hospital pharmacy to pick up study medications. Study evaluations must take place within the time window indicated on the Schedule of Evaluations (Section 5.1)

3. Clinical and Laboratory Assessments:

1. Laboratory evaluations will be performed at certified laboratories according to the study schedule. Required tests are specified in the Schedule of Evaluations (Section 5.1)
2. All subjects will undergo clinical assessment by the investigator or the investigator's designee in the manner and at the times specified in the Schedule of Evaluations (Section 5.1)
 1. Adverse events will be determined and defined according to Section 8 of the protocol
 2. Doses will be recorded of all immunosuppressants. The adjuvant immunosuppressant (mycophenolate or everolimus) will be counted and compared to the amount expected to be remaining based on the prescribed amount. An MPR will be calculated as follows: $(\text{Total Days' Supply in Period} / (\text{Last Fill Date} - \text{First Fill Date} + \text{Last Fill Days' Supply}))$
 3. Rejection and infection events will be recorded, as defined in Section 5.4)
 4. Hospitalization events will be determined by questioning the subject and review of hospital admissions in the EHR.
3. Graft function assessment will be monitored at regular intervals using the 4-variable abbreviated MDRD equation. It will be monitored at baseline and the end of the study for study outcomes and any time points dictated by standard of care follow-up in between those time points.

4. Definitions

1. Acute rejection is defined as a renal allograft biopsy showing grade 1A or greater, by the 1997 Banff Criteria and all updates since then. Biopsies will be performed when clinically warranted, based on changes in allograft function.
2. Rejection reversal is defined as return of serum creatinine to within 10% of baseline and/or histologic clearance by Banff Criteria
3. Resistant acute rejection is defined as no clinical or histologic improvement by renal biopsy within 7-10 days of initiation of treatment.
4. Recurrent acute rejection is defined as rejection recurring more than two weeks after documented rejection reversal.
5. Opportunistic Infections will be defined according the American Society of Transplant Recommendations for Screening, Monitoring, and

Reporting of Infectious Complications in Immunosuppression Trials in Recipients of Organ Transplantation (Appendix C1).

5. Treatment of Acute rejection:
 1. Acute rejection will be treated per institutional protocol, listed in Appendix C2.

6. Acceptable contraception methods

Option 1 (monotherapy methods):

1. Intrauterine devices (IUDs)
2. Tubal sterilization
3. Patient's partner had a vasectomy

Option 2 (Choice one from category A AND one from category B):

1. Category A:
 - a. Estrogen and progesterone
 - i. Oral contraceptive pill
 - ii. Transdermal patch
 - iii. Vaginal ring
 - b. Progesterone only
 - i. Injection
 - ii. Implant
 - c. Barrier method
 - i. Diaphragm with spermicide
 - ii. Cervical cap with spermicide
 - iii. Contraceptive sponge
2. Category B:
 - a. Male condom
 - b. Female condom
 - c. Diaphragm with spermicide (for use with hormone therapy)
 - d. Cervical cap with spermicide (for use with hormone therapy)
 - e. Contraceptive sponge (for use with hormone therapy)

7. Intervention Discontinuation Evaluations: At the scheduled time of intervention discontinuation (EOT, last date of study), the following evaluations must be completed: vital signs, clinical assessment, CBC, CHEM-7, Everolimus CO, Tacrolimus CO. In case of subject withdrawal from study, the patient will return to standard of care medications and request to continue with final assessment using MMAS-8, MMSE Scale and SF-36 will be discussed with a qualified team member.

8. Adverse Events

An adverse event (AE) is any untoward medical occurrence (i.e., any unfavorable and unintended sign [including abnormal laboratory findings], symptom or disease) in a subject or clinical investigation subject after providing written informed consent for participation in the study. Therefore, an AE may or may not be temporally or causally associated with the use of a medicinal (investigational) product. The occurrence of adverse events should be sought by non-directive questioning of the subject at each visit during the study. Adverse events also may be detected when they are volunteered by the subject during or between visits or through physical examination, laboratory test, or other assessments. Abnormal laboratory values or test results constitute adverse events only if they fulfill at least one of the following criteria:

1. they induce clinical signs or symptoms,
2. they are considered clinically significant,
3. they require therapy.

Clinically significant abnormal laboratory values or test results should be identified through a review of values outside of normal ranges/clinically notable ranges, significant changes from baseline or the previous visit, or values which are considered to be non-typical in subject with underlying disease. Investigators have the responsibility for managing the safety of individual subject and identifying adverse events. Adverse events should be recorded in the Adverse Events CRF with them accompanied by the following information:

1. severity of adverse events will be determined using the grading system outlined in the NCI Common Terminology Criteria for Adverse Events Version 4.03 (CTCAE), as it best fits the diagnostic terminology used in naming the event at the site clinical level.
2. possibility of relationship to the study treatment (no/yes)
3. its duration (start and end dates) or if the event is ongoing an outcome of not recovered or not resolved should be reported.
4. whether it constitutes a serious adverse event (SAE), if so report date should be provided
5. action taken regarding study treatment
6. whether other medication or therapies have been taken (concomitant medication/non-drug therapy)
7. its outcome (not recovered/not resolved; recovered/resolved; recovering/resolving, recovered/resolved with sequelae; fatal; or unknown)

An SAE is any adverse event which meets any one of the following criteria:

- An SAE is any adverse event that is life-threatening or that results in any of the following outcomes: death; in-patient hospitalization or prolongation of existing hospitalization; persistent or significant disability or incapacity; or a congenital anomaly or birth defect. Any other medical event that, in the medical judgment of the Principal Investigator, may jeopardize the subject or may require medical or surgical intervention to prevent one of the outcomes listed above is also considered an SAE. A planned medical or surgical procedure is not, in itself, an SAE. Also specifically excluded from this definition of SAE is any event judged by the Principal Investigator to represent progression of the malignancy under study, unless it results in death within the SAE Reporting Period.
- **Reporting of Serious Adverse Events.** Within 24 hours of first awareness of the event (immediately if the event is fatal or life-threatening), certain SAEs will be reported to Veloxis by ("SAEs," as defined below) that occur during the SAE reporting period (as defined below) in a Study subject assigned to receive the Veloxis Product. The subset of SAEs to be reported for this Study are those that fit into either of the following categories: (1) a death, regardless of whether it is considered related to treatment with the Veloxis Product, or (2) an SAE that is assessed by the Principal Investigator as both

related to treatment with the Veloxis Product and unexpected for that Product. An event should be considered "related" to the Veloxis Product if a relationship is at least a reasonable possibility, and "unexpectedness" should be based upon current Product labeling. Principal Investigator will report such SAEs using either Institution's Internal Adverse Event Report form or an FDA MEDWATCH form together with the Reportable Adverse Event Fax Cover Sheet provided by Veloxis. SAEs should be reported as soon as they are determined to meet the definition, even if complete information is not yet available.

- **SAE Reporting Period.** The SAEs that are subject to this reporting provision are those that occur from after the first dose of the Veloxis Product through 72 hours after discontinuation of the Veloxis Product. In addition, any and all related SAEs that occur after the reporting period of which the Principal Investigator becomes aware should also be reported.

-

AEs and SAEs will be reported in accordance with the FDA Guidelines for Post-Marketing Reporting of Adverse Events 21 CFR 314.80 and 21 CFR 600.80

<http://www.fda.gov/medwatch/report/regs.htm>. Any serious adverse event or a non-serious adverse event that is related to the study and unexpected will be reported to the FDA, per reporting guidelines, as soon as possible, but no later than 15 working days.. Further, all serious adverse events that are related to the study and are unexpected must be reported to The Medical University of South Carolina IRB within 10 days per The Medical University of South Carolina IRB Unanticipated Problems and Adverse Events Policy and Procedures reporting guidelines.

9. Criteria for intervention discontinuation

1. The intervention will be withheld/discontinued for AE of grade 3 or higher or if requested by the study participant.
2. Additionally, the intervention will be discontinued if the subject meets criteria for the following reasons:
 1. Pregnancy: If a woman becomes pregnant or a male's female partner becomes pregnant while on-study, the subject will be required to instruct investigators immediately.
 2. Loss of graft: Defined as death or need for retransplant. Patients will be deemed a treatment failure and the intervention will be discontinued.\

10. Statistical considerations

1. Outcomes
 1. Primary outcome- Treatment efficacy, defined difference in change from baseline to six month measure by MMAS-8 in both arms.
 2. Secondary objectives
 1. Secondary outcome- Safety outcomes of treatment failure rate, defined as acute allograft rejection with a Banff grade 1A or higher, graft loss, or death at one year post-conversion in both arms.

2. Sample size estimation for the primary outcome

- 1.** No formal power analysis conducted since this is a pilot study. However, the sample size proposed (n=40) would be able to observe a mean difference between groups in the change of MMAS-8 scores of 2 ± 2 points (95% CI 0.73,3.27) with 87% power. Additionally, a mean difference between groups in the change in the Memphis Side Effect Scale (MSES) of 5 ± 5 points (95% CI 1.83,8.17) would have 87% power in the current sample size. Given the average MSES score of 25 points in kidney transplant patients within 2 years of transplant, this appears to be a feasible outcome (11). In order to demonstrate noninferiority in treatment failure, it would require 400 subjects (200 in each group) to have 80% power, estimating a treatment failure rate of 20% and an acceptable difference of 10%. We expect that 70% of those approached meeting study inclusion/exclusion criteria will agree to participate and that 85% of those that consent and are enrolled in the study will complete all visits. If the 95% CIs for the actual enrollment and completion proportions are outside of these thresholds, then feasibility will not be met. If the 95% CIs encompass these expected values, then feasibility will be met.

3. Missing data and imputation methods

- 1.** Under the intention-to-treat principle, all subjects are included in the analysis. Extensive efforts will be made to keep all missing data to a minimum and minimize loss to follow-up (LTFU). However, it is likely that some missing data may occur.

11. Human subjects

1. Institutional review board (IRB) review and informed consent

- 1.** This protocol, the ICF, and any subsequent modifications must be reviewed and approved by the IRB. A signed and dated ICF must be obtained from the subject as defined in 21CFR50.3. The ICF must also be signed and dated by a member of the study staff qualified to be delegated the authority to obtain informed consent. A copy of the ICF must be given to the subject and the consent process must be documented in the subject's medical record. The PI or delegated sub-Investigator is responsible for ensuring that informed consent is obtained from each patient prior to conducting any study-related activities.

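### Exploratory item 4 gives a concrete measure for MPR only after cutting it at 80%; a full-scale comparison with a confidence interval should be stated beside it

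*Combined protocol and SAP*

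**What the plan says.** In Section 1 (Study Objectives), the list containing MPR opens with "Outcomes 3.3.2 through 3.3.11 are considered exploratory". Item 4 of that list reads "Examine the medication possession ratio (MPR) of adjunctive immunosuppressants (Everolimus or mycophenolate) during follow up between the two arms". Its single sub-item is "Compare the prevalence of patients with MPR >80" per cent. No source is given there for the 80% threshold.

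Section 5, under Clinical and Laboratory Assessments, introduces the formula with "An MPR will be calculated as follows". The numerator is "Total Days' Supply in Period". The denominator is the time from first to last fill plus the days' supply of the last fill. The result is a ratio for each subject, not a yes/no outcome.

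Section 10 (Statistical considerations) names no summary statistic, test or model for MPR. It states "No formal power analysis conducted since this is a pilot study", and its illustrative power figures cover only MMAS-8 and the side-effect scale. On size, Section 3 says "There will be 20 subjects in each arm, with a total study size of 40 subjects".

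The only adherence figures by dosing frequency are in Section 2, Supporting data, Table 1. The once-daily row is "QD (1 dose/d) 79 14 35-97" (mean, SD and range, in per cent); the twice-daily mean and SD are 69 and 15. The text there describes them as dose-taking compliance measured by electronic monitoring (MEMS), pooled from 76 studies across therapeutic areas.

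**The concern.** A cut at 80% scores a subject at 79% the same as one at 40%, and the opposite of one at 81%. If typical values lie near the threshold, as the once-daily mean in Table 1 would suggest, small differences decide the classification and large ones are ignored. With 20 subjects per arm there is little information to spare.

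The trial is open-label and its primary outcome, MMAS-8, is self-reported. MPR is the one adherence measure among the listed objectives that does not rest on self-report, so readers will look to it to corroborate the primary result. Section 2 also raises the possibility that pairing a once-daily with a twice-daily product lowers adherence to the latter, and adjunctive-drug MPR bears directly on that. If only the two proportions are reported, a null could be taken as failure to corroborate when part of the cause is the cut. A later trial would also lack an estimate of the MPR difference and its spread.

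**Working it through.** **Inputs.** 20 per arm (Section 3); 85% expected completion, so 0.85 × 20 = 17 per arm as a sensitivity case (Section 10); 79 ± 14 and 69 ± 15 (Section 2, Table 1). Assumptions: two-sided 5% level, since the protocol states none but uses 95% CIs; and Table 1 means and SDs used as a stand-in for subject-level MPR.

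**The plan's own figure.** The protocol states no power for MPR. Its MMAS-8 figure (difference 2, SD 2, 20 per arm, 87%) is reproduced: a two-sample t-test gives 86.9%, and the normal approximation Φ(2 / (2√(2/20)) − 1.96) = Φ(1.20) gives 88.5%.

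**Full-scale MPR.** Pooled SD = √((14² + 15²)/2) = 14.51. Normal approximation: Φ(10 / (14.51√(2/20)) − 1.96) = Φ(0.22) = 58.7%. The t-test gives 56.5%.

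**Cut at 80%, normal model.** P(MPR > 80) is 1 − Φ((80 − 79)/14) = 47.2% once daily and 1 − Φ((80 − 69)/15) = 23.2% twice daily.

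**Cut at 80%, beta model.** Beta distributions on 0–100% with the same means and SDs give 54.4% and 26.1%.

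Power at 20 per arm (the tests on the cut are exact calculations; the beta-model t-test and both Wilcoxon figures are simulated):

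| Model | t-test, full scale | Wilcoxon, full scale | Chi-square on cut | Fisher on cut |
|---|---|---|---|---|
| Normal | 56.5% | 54–55% | 36.4% | 25.8% |
| Beta | 56.9% | 59% | 44.4% | 33.2% |

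Loss from the cut, t-test minus test on the cut:
- Normal: 56.5 − 36.4 = 20.1 points (chi-square); 56.5 − 25.8 = about 31 (Fisher).
- Beta: 56.9 − 44.4 = 12.5 points (chi-square); 56.9 − 33.2 = 23.7 (Fisher).

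The range is therefore about 12 to 31 points. The Wilcoxon comparisons fall inside it.

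**At 17 per arm.** Normal: t-test 49.6%, chi-square 31.0%, Fisher 19.7%, so losses of 18.5 and 29.9 points. Beta: t-test 50.2%, chi-square 41.0%, Fisher 27.7%, so losses of 9.2 and 22.5 points.

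**Subjects for 80% power, normal model.** 34 per arm on the full scale against 62 for the proportion (70 with continuity correction).

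**Where the gain shrinks or reverses.**
- Beta model, same means, SD 20 in both arms, 17 per arm: t-test about 30–31%, chi-square about 31–32%, Wilcoxon 37.5%. The t-test gains nothing; Wilcoxon gains about 6 points.
- Two-group population (assumed: adherent subjects uniform on 88–100%, non-adherent uniform on 40–78%), with 90% against 55% adherent and 20 per arm: chi-square 75%, Fisher 63%, Wilcoxon 49%. With 80% against 45% adherent: 65%, 53% and 49%. Here the cut falls in the gap between the groups and has more power than Wilcoxon.

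**The case against.** The strongest reply is textual. A reader might infer that the above-80% proportion is the only between-arm comparison of MPR in the plan. It is not: the parent line of item 4 examines MPR itself between the arms, and the threshold is a sub-item. The side-effect scale and SF-36 items use the same verb, and nobody would read those as dichotomised. This stands. What remains is that the parent line names no statistic, so the only measure actually defined is the proportion. Section 10 also names no test for other outcomes, including the primary, so the omission is general; here, though, a lossy measure fills the gap.

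A reader might also take the power loss as following from the protocol's own expectations. The documents do not support that. Table 1 is background on doses taken by electronic monitor; MPR is a fill-based possession ratio that can exceed 100%. Table 1 does not say whether its SDs are between patients or between studies, and the protocol nowhere predicts 79% against 69% for MPR.

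Nor is MPR the only adherence information beyond self-report: Section 5 provides for counting the adjunctive drug and schedules drug levels. MPR is only the one listed as an objective.

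Finally, the two-group scenario shows that replacing the cut outright could lose power. That is a good reason to keep the proportion, but not a reason to leave the full-scale comparison undefined.

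**Conclusion.** The point holds as a cheap improvement of minor severity. The one MPR comparison with a defined measure discards information from a ratio already computed for each subject. The cost is roughly 12 to 31 points of power at 20 per arm if Table 1 stands in for subject-level MPR and the distribution is normal or beta. It is near zero against a t-test with a wider SD, and negative against Wilcoxon in a sharply split population. Since the documents give no MPR distribution, none of these sizes can be claimed for this trial.

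It would go too far to say that the plan's conclusions are undermined. MPR is exploratory in a 40-subject pilot, no stated power or decision rule rests on it, and even full-scale MPR has only about 54 to 59% power on the base-case inputs. A null on either scale would be weak evidence. The value of the change lies mainly in an effect estimate with its uncertainty.

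**What to change.** Add one sentence under exploratory item 4, repeated in Section 10, for example: *MPR of the adjunctive drug will be compared between arms on its full scale, using the Wilcoxon rank-sum test and a location-shift estimate with 95% CI; the proportion of subjects with MPR above 80% will be reported by arm alongside, with its 95% CI.* A difference in means or medians with a 95% CI would also serve, provided the choice is fixed before the data are seen.

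This needs no new data, visits or subjects. The costs are one more exploratory comparison and a location shift that is less familiar to clinicians than a percentage, which is why the proportion stays in the report.
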